#### **4.4. Lifestyle Considerations**

While enrolled in this study, subjects must agree to refrain from use of the prohibited medications and treatments listed in [Section 5.4](#) for the duration of the study.

#### **4.5. Protocol Deviations**

This study will be conducted as described in this protocol, except for emergency situations in which the protection, safety, and well-being of the subject requires immediate intervention, based on the judgment of the investigator (or a responsible, appropriately trained professional). In the event of a significant deviation from the protocol due to an emergency, accident, or mistake, the investigator or designee must contact Revance or designee by telephone at the earliest possible time. This will allow an early joint decision regarding the subject's continuation in the study. This decision will be documented by the investigator and Revance or designee.

#### **4.6. Pregnancy**

A female is of childbearing potential UNLESS she is post-menopausal (no menses for 12 consecutive months) or without a uterus and/or both ovaries.

All WOCBP must use an effective method of birth control throughout the study, (e.g., oral contraceptive pill, injection, implant, patch, vaginal ring, intrauterine coil, intrauterine device, tubal ligation, barrier method) used WITH an additional form of contraception (e.g., sponge, spermicide or condom); true abstinence (i.e. no heterosexual intercourse) or having a vasectomized partner is considered an acceptable method of contraception.

Before enrolling WOCBP in this study, investigators must review guidelines about study participation for WOCBP with the subject. The topics should generally include:

- ICF content
- Pregnancy prevention information
- Risks to unborn child(ren)
- Any drug interactions with hormonal contraceptives
- Contraceptives in current use
- Guidelines for the follow-up of a reported pregnancy

Prior to study enrollment, WOCBP must be advised of the importance of avoiding pregnancy during participation in this study and the potential risk factors for an unintentional pregnancy. The subject must sign the ICF stating that the above-mentioned risk factors for unintentional pregnancy and the consequences were discussed with her.

During the study, all WOCBP should be instructed to contact the investigator immediately (within 24 hours) if pregnancy is suspected (e.g., missed or late menstrual cycle). The investigator, or qualified designee, must immediately notify Revance or designee of any female subject who becomes pregnant any time during study participation, record the information on the Pregnancy Notification Form and send the form to Revance or designee. Subjects will remain enrolled in the study. The investigator will be asked to follow-up with a phone call with the subject periodically throughout the pregnancy and post-delivery as applicable for ongoing health and safety information, as applicable.

If an SAE occurs in conjunction with the pregnancy such as untoward outcome of the pregnancy or of the offspring (spontaneous abortion, or abnormality in the offspring) then the reporting time frame for an SAE must be met and SAE reporting procedures followed. In the event of a normal birth follow-up with the subject will occur with a phone call until the first well baby visit to ensure no SAEs are identified in the neonate, at which time active follow-up to the pregnancy will cease.

## 5. Study Intervention

The active pharmaceutical ingredient, DaxibotulinumtoxinA, is a purified 150 kilodalton (kDa) botulinum neurotoxin type A, derived from the Hall strain *C. botulinum*. Produced by *C. botulinum* as a single inactive polypeptide chain of 150 kDa, DaxibotulinumtoxinA undergoes proteolytic cleavage by proteases present in the fermentation culture to yield the active di-chain molecule comprised of a 100 kDa heavy chain and a 50 kDa light chain linked via both non-covalent interactions and a disulfide bond (Aoki 2001). The heavy chain plays a role in cell binding, internalization, and translocation of DaxibotulinumtoxinA into nerve cells. The light chain acts as a site-specific metalloprotease causing selective cleavage and inactivation of the 25 kDa synaptosome associated protein (SNAP-25) which is a cell membrane localized component of the vesicular release machinery. This cleavage of SNAP-25 by the light chain of botulinum toxin type A blocks the synaptic vesicle exocytosis and subsequent release of acetylcholine, thus leading to a dose-dependent weakening of the target muscle.

### 5.1. Study Intervention(s) Administered

This is an open-label, non-randomized study. All subjects will receive DAXI for injection as IM injections. A subject will receive 40 U of DAXI for injection in a standard 5-point injection paradigm in the GL-complex (procerus and corrugator muscles), 32 U of DAXI for injection in a 4-point injection paradigm in the frontalis muscle, and 48 U of DAXI for injection in a 3-point injection paradigm per side in the lateral canthal areas.

[figure not shown]

h: 1.0

0

[figure not shown]

### 5.3. Concomitant Medications/Therapies

Concomitant medications are any prescription or over-the-counter preparations used by subjects during participation in the study. Use of concomitant medications will be recorded on the Concomitant Medications electronic case report form (eCRF) beginning at the Screening Visit (and including anything taken during the previous 30 days) until the Final Evaluation Visit.

The dose and dosing regimen of all prescription and non-prescription therapies and medications, including herbs, vitamins, or other nutritional supplements administered will be documented.

## **6. Discontinuation of Study Intervention and Subject Discontinuation/Withdrawal**

### **6.1. Subject Discontinuation/Withdrawal from the Study**

A subject may voluntarily withdraw from study participation at any time. If the subject withdraws consent and discontinues from the study, the investigator will attempt to determine the reason for discontinuation and record the reason in the subject's study records and on the eCRF. If a subject withdraws consent because of an AE, that AE should be indicated as the reason for withdrawal. In the event of early discontinuation, (i.e., prior to the Final Evaluation) where consent was not withdrawn, the subject should be asked to return to the study center to complete the assessments specified in the Final Evaluation Visit. Subjects who withdraw from the study will not be replaced. Subjects who withdraw from the study, but agree to continued follow-up, must be reconsented by the investigator for this limited participation in the study (unless this situation was adequately described in the original ICF).

If at any time during the study, the investigator determines that it is not in the best interest of the subject to continue, the subject will be discontinued from participation. The investigator can discontinue a subject from study participation at any time if medically necessary or if the subject has failed to follow study procedures or keep follow-up appointments. Appropriate documentation in the subject's study record and eCRF regarding the reason for discontinuation must be completed. Prior to discontinuing a subject from study participation, the investigator will discuss his/her intentions with the Medical Monitor or designee.

All subjects who fail to return to the study center for the required follow-up visits will be contacted by phone to determine the reason(s) why the subject failed to return for the necessary visit or elected to discontinue from the study. If a subject is unreachable by telephone after a

minimum of two documented attempts (one attempt on two different days), a registered letter will be sent requesting that contact be made with the investigator.

Revance has the right to terminate or to stop the study at any time. Should this be necessary, both Revance and the investigator will ensure that proper study discontinuation procedures are completed.

## **6.2. Lost to Follow-up**

A subject will be considered lost to follow-up if he or she repeatedly fails to return for scheduled visits and is unable to be contacted by the study center.

Before a subject is deemed lost-to-follow-up, the study center should make every effort to contact the subject (see Section 6.1) and reschedule the missed visit as soon as possible. The subject should be counseled on the importance of visit compliance and should be questioned as to whether he or she wishes to continue in the study.

# **7. Study Assessments and Procedures**

## **7.1. Subject Entry Procedures**

Subject informed consent must be obtained prior to conducting screening procedures. Each signature must be personally dated by each signatory and the original retained by the PI as part of the study record. A signed copy must be provided to each subject (refer to [Section 4.3](#)).

## **7.2. Schedule of Visits and Procedures**

It is recommended that study visits be scheduled at approximately the same time of day throughout the trial. Subject assessments of GL, FHL, and LCL severity (ie, PFWS, PFHWS, and PLCWS) must be completed prior to investigator assessments (ie, IGA-FWS, IGA-FHLs, and IGA-LCWS). In addition, subjects should complete the PNA, P-GAIS, and Satisfaction with Treatment items prior to completing the FASE and FACE-Q assessments. The IGA-FHWS, IGA-FWS, IGA-LCWS, and Investigator GAIS should be performed by the same evaluator throughout the study. If it is not possible to use the same evaluator throughout the study, two evaluators should examine the subject together and discuss findings for at least 1 prior visit. The SOA is provided in [Section 1.3](#).

### **7.2.1. Screening Visit**

The Screening Visit must take place within 14 days prior to the treatment visit (Day 1 Visit).

The following procedures must be performed and recorded at this visit:

1. Review study procedures and information regarding the trial and obtain written informed consent and privacy authorization (as applicable).
2. Review eligibility criteria.
3. Obtain medical/surgical history, including prior toxin use, and demographic information, including Fitzpatrick skin phototype.

4. Conduct patient education: Discuss the potential effect of DAXI for injection treatment, explain the PFWS, PFHWS, and PLCWS measurements and the categories of the severity assessment scales, and instruct the subjects to consider depth of lines for GL, FHL, and LCL severity. Use the provided Patient Education Brochure.

9. Perform a physical examination,

11. Measure and record vital signs (body temperature, respiratory rate, sitting radial pulse, and sitting systolic and diastolic blood pressure); subjects should sit for 5 minutes prior to taking pulse and blood pressure.

13. Collect blood and urine samples for clinical safety laboratory tests (hematology, serum chemistry, PT, and urinalysis).

The Screening Visit clinical laboratory test results and UPT must be reviewed and signed by the investigator; any abnormal results must be determined to be not clinically significant by the investigator prior to enrollment.

### 7.2.2. Treatment Visit (Day 1)

The Treatment Visit (Day 1 Visit) must be performed within 14 days of the Screening Visit. The following procedures must be performed and recorded for each visit:

## Prior to Investigational Product Administration

1. Confirm that all screening procedures have been completed, results reviewed, and recorded.
2. Review eligibility criteria.
3. Update medical/surgical history.

7. Conduct patient education. Discuss the potential effect of DAXI for injection treatment, explain the PFWS, PFHWS, and PLCWS measurements and the categories of the severity assessment scales, and instruct the subjects to consider depth of lines for GL, FHL, and LCL severity. Use the provided Patient Education Brochure.

15. Measure and record vital signs (body temperature, respiratory rate, sitting radial pulse, and sitting systolic and diastolic blood pressure). Subjects must sit for 5 minutes prior to having pulse and blood pressure measurements taken.

[REDACTED]

17. Update concomitant therapy/medications since screening, documenting the dose and dosing regimen of all prescription and non-prescription therapies and medications, including herbs, vitamins, or other nutritional supplements (Section 5.3).

### **Investigational Product Preparation**

The assigned investigational product will be prepared by the trained dose preparer according to trial-specific instructions. The prepared investigational product will be provided in syringes to the investigator for administration.

### **Investigational Product Administration**

Investigational product will be administered by the investigator to injection sites in the designated treatment areas

[REDACTED]

### **After Investigational Product Administration**

[REDACTED] obtain vital signs (body temperature, respiratory rate, sitting radial pulse, and sitting systolic and diastolic blood pressures).

[REDACTED]

[REDACTED]

[REDACTED]

[REDACTED]

[REDACTED]

[REDACTED]

[REDACTED]

#### **7.2.3. Week 1 Follow-Up Phone Call**

At the Week 1 follow-up phone call, the subject will be contacted by the site staff for a health status check, concomitant therapy/medication check, and a query about AEs that may have occurred.

The following procedures must be performed and recorded:

1. Query subject about any new or ongoing AEs since the last visit

#### 7.2.4. Follow-up Visits

At Weeks 2, 4, 8, 12, 16, 20, 24, 28, and 32, the following procedures must be performed and recorded:

2. Conduct patient education: discuss the potential effect of DAXI for injection treatment, explain the PFWS, PFHWS, and PLCWS measurement and the categories of the severity assessment scales, and instruct the subjects to consider depth of lines for severity grading. Use the provided Patient Education Brochure.

14. Collect blood and urine samples for clinical safety laboratory tests (hematology, serum chemistry, and urinalysis) (Week 4 Visit only).

17. Assess any new or ongoing AEs since the last visit.

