## 1. Protocol Summary

### 1.1. Synopsis

**Title** A Phase 2, Multicenter, Open-Label Study to Evaluate the Efficacy and Safety of DaxibotulinumtoxinA for Injection (DAXI for Injection) for the Combined Treatment of Upper Facial Lines (Glabellar Lines, Dynamic Forehead Lines and Lateral Canthal Lines)

**Study Description:** This is a Phase 2, multicenter, open-label, single-arm study to evaluate the safety and efficacy of DaxibotulinumtoxinA for injection (DAXI for injection) in the treatment of glabellar lines (GL), dynamic forehead lines (FHL), and lateral canthal lines (LCL).

Approximately 48 subjects (18 years of age and above) with moderate to severe GL, FHL, and LCL (all assessed at maximum contraction) will be screened for eligibility and enrolled to receive a single treatment of DAXI for injection to be injected into 5 GL sites, 4 FHL sites, and 3 LCL sites per side (total of 6 LCL sites).

All subjects will be assigned to receive DAXI for injection.

The principal investigator (PI) at each clinical site will utilize a standard 5-point injection paradigm when injecting GL-complex (procerus and corrugator muscles), a 4-point injection paradigm when injecting the frontalis muscle, and a 3 point-injection paradigm when injecting the lateral canthal area bilaterally.

The primary objective of this study is to determine the efficacy and safety of the combined treatment of three upper facial regions with DAXI for injection.

The efficacy response for GL is the proportion of subjects reporting an improvement in severity defined as achieving a score of 0 (none) or 1 (mild) at Week 4, at maximum contraction (maximum frown) on the Investigator Global Assessment Frown Wrinkle Severity (IGA-FWS) scale and separately, on the Patient Frown Wrinkle Severity (PFWS) scale.

The efficacy response for FHL is the proportion of subjects reporting an improvement in severity defined as achieving a score of 0 (none) or 1 (mild) at Week 4, at maximum contraction (maximum eyebrow elevation) on the Investigator Global Assessment Forehead Wrinkle Severity Scale (IGA-FHWS) scale and separately, on the Patient Forehead Wrinkle Severity (PFHWS) scale.

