**Endpoints:**

Key Endpoints

- The proportion of subjects achieving a score of 0 (none) or 1 (mild) in GL severity at maximum contraction at Week 4 as assessed by the IGA-FWS
- The proportion of subjects achieving a score of 0 (none) or 1 (mild) in FHL severity at maximum contraction at Week 4 as assessed by the IGA-FHWS
- The proportion of subjects achieving a score of 0 (none) or 1 (mild) in LCL severity at maximum contraction at Week 4 as assessed by the IGA-LCWS

Safety Evaluations:

- Vital signs
- Physical examination
- [REDACTED]
- Injection site evaluation
- Concomitant therapies/medications
- Clinical laboratory tests (hematology, serum chemistry, prothrombin time [PT], urinalysis)
- [REDACTED]
- Adverse events (AEs)
- Incidence, severity, and relationship to study drug of treatment-emergent AEs (TEAEs) and serious adverse events (SAEs) during the overall study duration.

Evaluations:

- FACE-Q™
  - FACE-Q™ Appraisal of Lines: Overall
  - FACE-Q™ Appraisal of Lines: Forehead
  - FACE-Q™ Appraisal of Lines: Between Eyebrows
  - FACE-Q™ Appraisal of Lines: Crow's Feet Lines
  - FACE-Q™ Satisfaction with Forehead and Eyebrows
  - FACE-Q™ Psychological Function
  - FACE-Q™ Satisfaction with Outcome
- Facial Age Self Evaluation (FASE)
- Global Aesthetic Improvement Scale (GAIS-Subject and Investigator)
- Subject Global Satisfaction with Treatment
- Patient Naturalness Assessment (PNA)
- Photography of treatment areas including standardized image capture of right, left, and frontal views at rest and at maximum contraction (frown, smile, and forehead elevation); and standardized video capture of frontal and oblique views at maximum contraction (frown, smile, and forehead elevation).

**Study Population:** Approximately 48 male and female subjects aged 18 and over years of age.

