### 7.2.5. Final Evaluation Visit (Week 36) or Early Discontinuation

The following procedures must be performed and recorded at the Final Evaluation Visit for each subject. Following treatment, subjects will be followed until Week 36, or until the time when severity scores for GL, FHL, and LCL return to baseline (Day 1 pretreatment) or worse, based on both the investigator and subject evaluations (minimum of 24 weeks and up to 36 weeks after treatment), whichever occurs first. Subjects will then have a Final Evaluation Visit at which time the following procedures must be performed:

patient education: discuss the potential effect of DAXI for injection treatment, explain the PFWS, PFHWS, and PLCWS measurement and the categories of the severity assessment scales, and instruct the subjects to consider depth of lines for severity grading. Use the provided Patient Education Brochure.

8. Perform a physical examination

14. Measure and record vital signs (body temperature, respiratory rate, sitting radial pulse, and sitting systolic and diastolic blood pressure).

16. Collect blood and urine samples for clinical safety laboratory tests (hematology, serum chemistry, and urinalysis).

If there are no safety concerns, the subject's participation in the study is complete at this visit.

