#### **7.4.1.2. Assessment and Reporting Requirements**

The investigator will assess each subject post-treatment and at each subsequent study visit for the occurrence of AEs. In order to avoid bias in eliciting AEs, subjects should be asked the following non-leading question: "How have you felt since your last visit?" All AEs (serious and non-serious) will be collected from the signing of the ICF until the Final Evaluation Visit. Any AE reported by the subject must be recorded on the source documents and eCRFs.

All AEs will be collected after IP administration until Week 36 or the Final Evaluation Visit at all timepoints as specified in the SOA ([Section 1.3](#)). Medical occurrences related to protocol-mandated intervention that begin before the start of study intervention but after obtaining informed consent will be recorded as AEs.

[figure not shown]
All SAEs will be recorded and reported to Revance or designee immediately within 24 hours of their awareness of the event. All fatal or life-threatening SAEs should be telephoned to Revance or the designee's authorized representative as soon as the investigator learns of the event.

[figure not shown]

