#### **8.3.1. Efficacy Analyses**

In general, descriptive summaries will include means, standard deviations, median, lower and upper quartiles, and ranges for continuous variables; and counts and proportions for categorical measures. Kaplan-Meier curves will be plotted for each time-to-event endpoint and median duration with associated 95% CIs will be provided. Proportion of subjects with response at a given time point will be reported based on observed cases, as well as based on proportion of treated subjects. As this is an open-label study with no placebo comparator arm, no formal hypothesis tests are planned.

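### Post-treatment patient education repeats a discussion of the drug's potential effect in the step that explains the self-rating scales, an avoidable source of expectation bias in the patient-rated outcomes (minor)

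*Protocol*

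**What the plan says.** Protocol section 7.2.4 opens with "At Weeks 2, 4, 8, 12, 16, 20, 24, 28, and 32, the following procedures must be performed and recorded". Item 2 of its list begins "Conduct patient education: discuss the potential effect of DAXI for injection treatment" and goes on, in the same item, to explain the PFWS, PFHWS and PLCWS and their categories, to tell subjects to consider line depth, and to call for the Patient Education Brochure. Section 7.2.5 carries the same instruction for the Final Evaluation Visit: "patient education: discuss the potential effect of DAXI for injection treatment".

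The same education, including the effect discussion, is also listed before treatment, in section 7.2.1 (item 4) and section 7.2.2 (item 7). At the Week 1 phone call "the subject will be contacted by the site staff for a health status check", and no education step is visible there.

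The patient scales are used in two places. The synopsis defines the glabellar response on the investigator scale "and separately, on the Patient Frown Wrinkle Severity (PFWS) scale", with parallel wording for the forehead and lateral canthal lines. Section 3.1 lets a subject complete the study from Week 24 once scores in all three areas are back to baseline or worse on both investigator and subject ratings.

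The three key endpoints are investigator ratings; the first, for example, is the 0 or 1 proportion "in GL severity at maximum contraction at Week 4 as assessed by the IGA-FWS". Section 8.3.1 adds: "As this is an open-label study with no placebo comparator arm, no formal hypothesis tests are planned".

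**The concern.** A self-rating should reflect what the subject sees in the mirror. Talking about what the product may do, at the visit where the subject grades the result, adds a cue that is not about the wrinkles. It comes on top of the expectation already present in an open-label study. Explaining the scales is legitimate rater training and needs repeating. The effect discussion has already been held twice before treatment, and the protocol gives no reason for holding it again afterwards.

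Two things are at stake: the patient-rated 0 or 1 proportions at Week 4, which the synopsis presents as separate efficacy responses, and the subject half of the rule that ends follow-up from Week 24. A control arm exposed to the same discussion would let part of such an effect cancel. Here nothing cancels it.

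**Working it through.** The protocol states no figure on this point, so there is none to reproduce. The check is mainly textual.

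**1. How often.** Section 7.2.4 covers Weeks 2, 4, 8, 12, 16, 20, 24, 28 and 32, which is 9 visits. Section 7.2.5 adds the final visit: 9 + 1 = up to 10 on-site post-treatment visits. The Week 1 call is excluded.

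**2. Whether the discussion is kept apart from the rating.** Sections 7.2 and 7.3 contain two ordering rules. Subject severity ratings come before investigator ratings, and the naturalness, patient GAIS and satisfaction items come before FASE and FACE-Q. Neither rule places education relative to rating. The effect discussion shares an item with the scale explanation, which is useful only before rating, so it probably comes first. The rating items are absent from the public text, so this order is likely but not proven.

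**3. Which ratings.** A Week 4 response requires patient scale ratings at Week 4. The return-to-baseline rule requires them from Week 24. Both fall at visits where education is required. The visit timing of GAIS, satisfaction, naturalness, FASE and FACE-Q is deferred to the schedule of assessments, which is not shown, so no claim is made about those instruments visit by visit.

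**4. Scale of a shift.** Input: N = 48 (section 8.1). If k subjects score 1 instead of 2, the response proportion rises by k/48:

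| k | k/48 |
|---|---|
| 1 | 2.1 points |
| 2 | 4.2 points |
| 3 | 6.25 points |
| 5 | 10.4 points |

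The values of k are assumed. The protocol gives no basis for choosing one.

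**5. Whether the planned summaries would show it.** Exact (Clopper-Pearson) 95% intervals at assumed response counts:

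| Responders | 95% interval |
|---|---|
| 29/48 | 45.3% to 74.2% |
| 34/48 | 55.9% to 83.0% |
| 38/48 | 65.0% to 89.5% |
| 43/48 | 77.3% to 96.5% |

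These describe sampling error only. A systematic shift moves the whole interval and leaves no trace in it.

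**6. Effect on follow-up.** Early completion needs three areas and two raters all back at baseline. A subject score held below baseline severity can only keep the subject in the study longer, by at most 36 − 24 = 12 weeks, and only when the subject's rating is the last condition unmet.

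**The case against.** Much of the case on the other side stands.

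- **Content and direction.** A reader might infer that staff repeatedly prompt subjects about expected benefit. The text does not support that. Its adjective is potential, and it does not mention benefit. The discussion could cover onset, waning, variability or unwanted effects, and the brochure is not shown. A push toward improvement is plausible early on; talk of waning later could act the other way.
- **Main results.** A reader might infer that the trial's principal efficacy results are compromised. They are not directly affected: all three key endpoints are investigator-rated, and no hypothesis test depends on the patient scales.
- **Size.** It is tempting to attach a figure. If 5% to 10% of all 48 subjects shifted, that would be 2.4 to 4.8 subjects. If the same share applied only to borderline subjects, and 12 were borderline, it would be 0.6 to 1.2 subjects (1.25 to 2.5 points); with 24 borderline, 1.2 to 2.4 subjects (2.5 to 5 points). Every input is invented, so none of these is an estimate.
- **Contradiction.** For adverse events section 7.4.1.2 says "In order to avoid bias in eliciting AEs, subjects should be asked the following non-leading question". This shows that the protocol recognises the risk of leading subjects. It is not an internal contradiction, because an open question and an anchored scale are different instruments.
- **Existing safeguards.** Sections 7.3.1 to 7.3.3 ask for severity at the time of rating, without comparison to the pre-treatment level. The categories are anchored, a mirror is used, and subjects rate before the investigator. These limit suggestion but do not remove it.
- **Increment.** Subjects know they received active drug and heard the discussion twice before treatment. Most expectation bias comes from the open-label design, and nothing shows how much the repetition adds.
- **Uniformity.** One script at every visit keeps administration consistent. That supports repeating the scale instruction, not the effect discussion.

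What survives is that the repeated discussion has no evident purpose after treatment and that nothing visible keeps it away from the self-ratings.

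**Conclusion.** The point holds in limited form and is minor. At up to 10 on-site post-treatment visits, a discussion of the drug's potential effect is built into the step that prepares subjects to use the PFWS, PFHWS and PLCWS. In a study with no control arm, this is an avoidable source of expectation bias in the patient-rated responses and in the subject part of the return-to-baseline rule, and it cannot be corrected in the analysis. Direction and size cannot be determined from the protocol; the only firm quantity is 2.1 points per subject moved from 2 to 1 at N = 48.

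The conclusion assumes that the discussion takes place as written and that no hidden text in the visit lists or schedule of assessments places it after the self-ratings. If such text exists, the concern largely falls away.

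**What to change.** In sections 7.2.4 and 7.2.5, delete the clause on discussing the potential effect of the product and keep the neutral explanation of the scales, their categories and line depth. Alternatively, keep the discussion but state that it takes place only after the subject has completed all self-ratings for that visit, and add this to the ordering rules in sections 7.2 and 7.3. Leave the discussion at screening and Day 1 as it is.

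The cost is one clause in two sections and, if the brochure covers drug effect, a scales-only version for post-treatment visits. Dose, visit schedule, safety procedures and sample size do not change. The expectation inherent in an open-label single-arm design remains and should be acknowledged when the patient-rated results are reported.
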